6.1.2.1 Optimal Biological Dose (OBD)

If positive tumor PK and PD effects are observed in patients treated at a specific dose, but no DLT is observed, dose escalation will continue as planned in order to demonstrate whether an increase in biological effect can be observed with increasing dosage or if such effect is maximized (ie, the OBD is attained). If the OBD has been achieved with <2 DLTs out of 6 patients, the OBD cohort will be expanded to an additional 8 patients to assure safety and to evaluate time course of PK and PD effects at 2 time cohorts (i.e., 2 ± 1 h and 24 ± 1 h), with 4 patients in each time cohorts, following the administration of the final dose on Day 5.

6.1.3 Dose Limiting Toxicity for Phase 0 or Phase 2

Dose limiting toxicity (DLT) will be defined as adverse event(s) which is/are attributable to the study treatment and unrelated to disease, disease progression, inter-current illness, or concomitant medications during the first 5 days in Phase 0 or in the first cycle (28 days) of Phase 2. The

maximum tolerated dose of ribociclib+everolimus will be that dose at which fewer than one-third of patients experience a dose limiting toxicity within each Phase. If multiple toxicities are seen, the presence of dose limiting toxicity should be based on the most severe toxicity experienced.

Table 9 DLT Criteria

TOXICITY	DLT CRITERIA
Hematology	CTCAE grade 4 neutropenia for more than 7 consecutive days CTCAE grade 4 thrombocytopenia CTCAE grade 3 thrombocytopenia with bleeding Grade 4 granulocytopenia lasting ≥ 5 days without hematopoietic growth factor support Febrile neutropenia (decrease in neutrophils associated with fever ≥ 38.5°C, ANC < 1.0 x 10 ⁹ /L)
Gastro-intestinal	≥ CTCAE grade 3 vomiting or nausea ≥ 48 hrs despite optimal anti-emetic therapy ≥ CTCAE grade 3 diarrhea ≥ 48 hrs despite optimal anti-diarrhea treatment
Hepato-biliary	CTCAE grade 2 bilirubin for more than 7 consecutive days ≥ CTCAE grade 3 total bilirubin ≥ CTCAE grade 2 ALT with a ≥ grade 2 bilirubin elevation of any duration in the absence of liver metastases ≥ CTCAE grade 3 ALT for more than 4 consecutive days CTCAE grade 4 ALT or AST CTCAE grade 4 serum alkaline phosphatase > 7 consecutive days
Cardiac	Cardiac toxicity ≥ CTCAE grade 3 Clinical signs of cardiac disease, such as unstable angina or myocardial infarction, or Troponin ≥ CTCAE grade 3
ECG QT Interval	QTcF interval ≥ 501 ms on at least two separate ECGs
Renal	≥ CTCAE grade ≥ 3 serum creatinine

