Stomatitis	CTCAE Grade 4
Non-infectious pneumonitis	CTCAE Grade 4
Metabolic events (hyperglycemia, dyslipidemia)	CTCAE Grade 4
Non-hematologic events	Inability to receive the subsequent planned dose due to toxicity Inability to begin the next cycle of treatment (at full dose) within 2 weeks of the scheduled dose due to unresolved toxicity Grade ≥ 2 non-hematological toxicity that persists beyond the first 42 days that in the judgment of the Principal Investigator is dose-limiting Certain Grade 2 toxicity (e.g. renal neurological, cardiovascular, gastrointestinal) which in the judgment of the Principal Investigator is dose-limiting ≥ CTCAE grade 3, except for the exclusions noted below:
Exceptions to DLT criteria	< 5 days of CTCAE grade 3 fatigue Untreated nausea or vomiting, or alopecia Grade 3 laboratory abnormalities that are responsive to oral supplementation or deemed by the investigator to be clinically insignificant
CTCAE version 4.03 will be used for all grading. Optimal therapy for vomiting or diarrhea will be based on institutional guidelines, with consideration of the prohibited medications listed in this protocol.	

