6.2.1 General guidelines for dose modifications

- For grade 1 and tolerable grade 2 treatment-related toxicities, with the exception of pneumonitis, patients may continue at the current dose of ribociclib+everolimus treatment.
- For intolerable grade 2 treatment-related toxicities as those that are irreversible (e.g., neurotoxicities, ocular toxicities, or cardiac toxicities) or prolonged grade 2 toxicities (i.e., those lasting longer than 14 days), or any grade 3 toxicities, with the exception of pneumonitis, dosing should be interrupted until resolution to grade 1 or lower followed by resumption of a new 28 days regimen. Dosing reductions could also be considered after grade 3 toxicities ([Table 11](#)).
- For any grade 4 toxicity, dosing should be interrupted and the patients should be followed until the toxicity resolution to baseline levels, grade 1, or become stable. Following recovery from grade 4 events, **no additional ribociclib+everolimus treatment** should be given to the patient except for neutropenia and thrombocytopenia (details in [Table 11](#)).

More detailed ribociclib and everolimus dose modification guidelines are described in Section [6.2.2](#) respectively for selected toxicities. Any variance from these guidelines in view of patient safety must first be discussed with the Sponsor unless there is an urgent need for action.

Initial Version date: 10/16/2018

Revision date: 03/11/2019, 5/07/2019, 09/26/2019, 03/17/2020, 08/26/2024

All dose modifications, interruptions or discontinuations must be based on the worst preceding toxicity as graded by the NCI Clinical Toxicity Criteria version 4.03.

Patients whose treatment is interrupted or permanently discontinued due to an AE must be followed until resolution or stabilization of the event. Patients with more than 1 interruption should be discontinued from ribociclib treatment.

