6.2.3 Follow-up for toxicities

An unscheduled visit should be performed in all cases below where toxicity monitoring is recommended more frequently than defined by the schedule of assessments.

Ongoing SAEs at the final safety evaluation visit or the end of study treatment visit (whichever is later) should be followed until they improve becoming non-serious events, stabilize, or return to baseline levels. Refer to [Section 8.2](#) for SAE.

Table 11 Criteria for post-tumor resection interruption and re-initiation of ribociclib+everolimus treatment

Worst toxicity (CTCAE 4.03 Grade)*	Regimen Modifications for Ribociclib Management Recommendations	Regimen Modifications for Everolimus Management Recommendations
HEMATOLOGICAL		
Anemia		
Grade 1 (Hemoglobin (Hgb) <LLN - 10.0 g/dL; <LLN - 6.2 mmol/L; <LLN - 100 g/L)	Continue regimen	Continue regimen
Grade 2 (Hgb <10.0 - 8.0 g/dL; <6.2 - 4.9 mmol/L; <100 - 80g/L)	Continue regimen	Continue regimen
Grade 3 (Hgb <8.0 g/dL; <4.9 mmol/L;	Dose interruption until recovery to grade ≤ 1. Re-initiate ribociclib at the same dose.	Dose interruption until recovery to grade ≤ 1. Re-initiate everolimus at the same dose.
Grade 4 (transfusion indicated Life-threatening)	Discontinue ribociclib	Discontinue everolimus
Neutropenia (ANC)		
Grade 1 (ANC < LLN - 1.5 x 10 ⁹ /L)	Continue regimen	Continue regimen
Grade 2 (ANC < 1.5 and ≥ 1.0 x 10 ⁹ /L)	Continue regimen	Continue regimen
Grade 3 (ANC < 1.0 and ≥ 0.5 x 10 ⁹ /L)	Dose interruption until recovery to ≥1.0x10 ⁹ /L (≤grade 2). Re-initiate ribociclib at the same dose level. If toxicity recurs at grade 3, temporary dose interruption until recovery to ≥1.0x10 ⁹ /L (≤grade 2). If resolved in ≤7 days, then maintain dose level. If resolved in >7 days, then reduce ribociclib dose to the next lower dose level.	Dose interruption until recovery to grade ≤2. Re-initiate everolimus at the same dose level. If ribociclib is interrupted/ discontinued, everolimus should also be interrupted/discontinued. Resume everolimus at same dose level if ribociclib is resumed at either the same or lower dose.
Grade 4 (ANC < 0.5 x 10 ⁹ /L)	Dose interruption until recovery to ≥1.0x10 ⁹ /L. Re-initiate ribociclib at the next lower dose level. If toxicity recurs at grade 4, discontinue ribociclib+everolimus	Dose interruption until recovery to grade ≤2. Re-initiate everolimus at the next lower dose level. If toxicity recurs at grade 4, discontinue ribociclib+everolimus

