Febrile neutropenia Grade 3 (ANC < 1.0 x 10 ⁹ /L, with a single temperature of ≥ 38.3 °C (101°F) or a sustained temperature of ≥ 38 °C (100.4°F) for more than one hour)	Dose interruption until improvement of ANC ≥1.0x10 ⁹ /L (≤Grade 2) and no fever. Restart at the next lower dose level. If febrile neutropenia recurs, discontinue ribociclib +everolimus.	Dose interruption until improvement of ANC ≥1.0x10 ⁹ /L (≤Grade 2) and no fever. Re-initiate everolimus at the next lower dose level. If febrile neutropenia recurs, discontinue ribociclib +everolimus.
Febrile neutropenia Grade 4 Life-threatening consequences; urgent intervention indicated	Discontinue treatment.	Discontinue treatment.

Worst toxicity (CTCAE 4.03 Grade)*	Regimen Modifications for Ribociclib Management Recommendations	Regimen Modifications for Everolimus Management Recommendations
Thrombocytopenia		
Grade 1 (PLT < LLN - $75 \times 10^9/L$)	Continue regimen	Continue regimen
Grade 2 (PLT < 75 and $\geq 50 \times 10^9/L$)	Dose interruption until recovery to grade ≤ 1 . Re-initiate ribociclib at the same dose.	Dose interruption until recovery to grade ≤ 1 . Re-initiate everolimus at the same dose.
Grade 3 (PLT < 50 and $\geq 25 \times 10^9/L$)	Dose interruption until recovery to grade ≤ 1 . Re-initiate ribociclib at the same dose level. If toxicity recurs at grade 3, temporary dose interruption until recovery to grade ≤ 1 and reduce ribociclib to the next lower dose level.	Dose interruption until recovery to grade ≤ 1 . Re-initiate everolimus at the next lower dose level. If toxicity recurs at grade 3, temporary dose interruption until recovery to grade ≤ 1 and reduce everolimus to the next lower dose level.
Grade 4 (PLT < $25 \times 10^9/L$)	Dose interruption until recovery to grade ≤ 1 . Re-initiate ribociclib at the next lower dose level. If toxicity recurs at grade 4: discontinue ribociclib	Dose interruption until recovery to grade ≤ 1 . Re-initiate everolimus at the next lower dose level. If toxicity recurs at grade 4: discontinue everolimus

Worst toxicity (CTCAE 4.03 Grade)*	Regimen Modifications for Ribociclib Management Recommendations	Regimen Modifications for Everolimus Management Recommendations
HEPATOTOXICITY (BILIRUBIN, SGPT/ALT, SGOT/AST)		
Total Bilirubin** without ALT/AST increase above baseline value (for patients with Gilbert Syndrome these dose modifications apply to changes in direct (conjugated) bilirubin only)		

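### Table 9 does not count treatment-related Grade 4 anemia as a DLT, although the protocol permanently stops both drugs for it in Phase 2

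*Combined protocol and SAP*

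**What the plan says.** **DLT definition.** Section 4.1.1 refers to Table 9 for the detailed DLT definition. The text of Section 6.1.3 sets attribution to study treatment and the window (five days in Phase 0, the 28 days of Cycle 1 in Phase 2), but no grade. The Hematology row starts with "CTCAE grade 4 neutropenia for more than 7 consecutive days CTCAE grade 4 thrombocytopenia CTCAE grade 3 thrombocytopenia with bleeding" and then adds prolonged Grade 4 granulocytopenia and febrile neutropenia. No row names anemia or hemoglobin.

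**The row for non-hematologic events.** This row holds a Grade 3-or-higher catch-all and two criteria on inability to continue: "Inability to receive the subsequent planned dose due to toxicity" and "Inability to begin the next cycle of treatment (at full dose) within 2 weeks of the scheduled dose due to unresolved toxicity".

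**Treatment rules in Phase 2.** Table 11 lists "Grade 4 (transfusion indicated Life-threatening" under anemia and discontinues both ribociclib and everolimus. Section 6.2.1 says that after a Grade 4 event no more study treatment "should be given to the patient except for neutropenia and thrombocytopenia". Anemia is not among the exceptions. After a first Grade 4 thrombocytopenia, Table 11 allows both drugs to restart at the next lower level.

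**Decision rule.** Under Section 4.1.2 and footnote a of Table 7, more than one DLT in six Phase 2 patients stops the level, and the next lower level becomes the RP2D.

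**The concern.** A DLT definition should capture the drug toxicities that the protocol itself regards as ending treatment. Here the ordering is reversed for two cytopenias. Grade 4 thrombocytopenia is a DLT even though the patient may be re-treated. Grade 4 anemia takes the patient off both drugs for good and is not counted.

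What is at stake is the RP2D, a secondary endpoint. Two of six patients at a level could come off both drugs in Cycle 1 because of drug-related, life-threatening anemia, and the level would still show no DLTs from those events. More realistically, one such patient could decide whether a level stands at one DLT in six (acceptable) or two in six (drop a level).

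The event is plausible. Section 6.1.5 asks for special attention to cytopenias. Section 1.2.2.3 lists anemia among treatment-related Grade 3-4 events with an incidence of at least 2%, although that is for everolimus plus exemestane in breast cancer. It is not specific to Grade 4 or to the first 28 days.

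**Working it through.** **Step 1. The texts side by side.**

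| Event, related to study drug, Phase 2 Cycle 1 | Table 11 / Section 6.2.1 | Table 9, read by row |
|---|---|---|
| Grade 4 thrombocytopenia | Hold, restart one level lower | DLT |
| Grade 4 neutropenia | Hold, restart one level lower | DLT if it lasts more than 7 days |
| Grade 4 anemia | Both drugs stopped permanently | Not listed |

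The listed exceptions to the DLT criteria cover short Grade 3 fatigue, untreated nausea or vomiting, alopecia, and certain Grade 3 laboratory abnormalities. They do not deal with Grade 4 anemia either way.

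**Step 2. The plan's own threshold.** Sections 3 and 9.5 define the MTD as the highest dose without a DLT in more than 17% of participants. 1/6 = 16.7%, which is not above 17%. 2/6 = 33.3%, which is. The threshold therefore agrees with the limit of one DLT in six, and a single event counted or left out can cross it.

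**Step 3. Effect on the Phase 2 rule.** Inputs are the rate r of all other DLTs and the rate q of treatment-related Grade 4 anemia in Cycle 1. The documents give neither, so both are assumed, and the two kinds of event are taken as independent.

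- DLT probability per patient with anemia counted: p = 1 − (1 − r)(1 − q).
- Chance of more than one DLT in six: 1 − (1 − p)^6 − 6p(1 − p)^5.

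For r = 10% and q = 0, p = 0.100 and the chance is 1 − 0.5314 − 0.3543 = 0.114. For q = 1%, 2% and 5%, p = 0.109, 0.118 and 0.145.

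| Other DLTs (r) | Anemia not counted | q = 1% | q = 2% | q = 5% |
|---|---|---|---|---|
| 5% | 3.3% | 4.5% | 5.9% | 10.9% |
| 10% | 11.4% | 13.2% | 15.1% | 21.2% |
| 15% | 22.4% | 24.4% | 26.4% | 32.6% |

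With only three patients at a level and r = 10%, the chance of two or more DLTs is 2.8% without anemia and 3.3%, 3.8% or 5.7% with it.

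Two or more Grade 4 anemias in six patients, with no other DLT involved, has probability 0.15%, 0.57% or 3.3% at q = 1%, 2% or 5%. The omission matters mainly where an anemia would be added to another DLT.

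**Step 4. How often six patients are reached.** Section 9.7.1 expects at most 3 to 12 Phase 2 patients and assumes that at most half of Phase 0 patients qualify. A level with three to six Phase 0 patients then gives about 1.5 to 3 in Phase 2. A level expanded by 8 gives about 14 × 0.5 = 7. Only an expanded level is likely to reach six.

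**The case against.** The strongest reply is that this is a choice and not an error. Ending one patient's treatment and counting a DLT serve different purposes, and nothing in the protocol says that the two lists must coincide. Much of the ribociclib safety background is blacked out, so a reason for leaving anemia out may exist where a public reader cannot see it. That also means the missing rate cannot be held against the plan.

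Safety is covered in other ways as well. Hemoglobin must be at least 9.0 g/dL at entry, both drugs stop at Grade 4, a life-threatening event is an SAE reportable within 24 hours, and the DSMB can recommend modification or termination. Phase 2 is exploratory and small. All of this stands and keeps the point minor. It does not remove it, because neither SAE reporting nor DSMB review sets the DLT count that fixes the RP2D, and the visible text gives no reason for treating the two Grade 4 cytopenias in reverse order.

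A reader might infer something stronger: that Table 9 is truly ambiguous, because the two inability criteria speak of toxicity without qualification, while a neighboring one spells out "non-hematological toxicity that persists beyond the first 42 days that in the judgment of the Principal Investigator is dose-limiting". On that view investigators could count Grade 4 anemia either way. The documents do not support this. The row label is the ordinary guide to what the row covers. Ignoring it would turn routine Table 11 holds into DLTs. For Grade 3 neutropenia the instruction after recovery is "Re-initiate ribociclib at the same dose level. If toxicity recurs at grade 3, temporary dose interruption until recovery to" a set count, and for Grade 2 thrombocytopenia it is "Re-initiate ribociclib at the same dose". Counting those holds would contradict the Hematology row's own thresholds. The repeated qualifier is weak evidence in a table with other redundancies, such as the doubled grade sign in the renal row. Read by its labels, the table gives a clear answer: Grade 4 anemia is not a DLT.

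**Conclusion.** The point holds as a minor one. On the coherent reading of Table 9, treatment-related Grade 4 anemia falls outside the DLT count, which does not fit with the protocol's own decision to end both drugs for it.

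At an assumed 10% rate of other DLTs and six patients, counting it would raise the chance of stopping a level by about 2 to 4 percentage points for anemia rates of 1% to 2% (11.4% to 13.2% or 15.1%), and by about 10 points at 5% (to 21.2%). These figures rest on assumed rates and independence.

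The effect is mainly limited to Phase 2 levels that reach six patients. It would be wrong to infer that Phase 0 escalation is materially affected: its window is five days, and the Table 11 stopping rule applies only after resection. It would also be wrong to infer that affected patients go unprotected. Post-operative anemia that is not attributable to study drug would not count as a DLT in any case.

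**What to change.** Add one line to the Hematology row of Table 9: treatment-related CTCAE Grade 4 anemia. The Phase 2 rule then counts an event for which the protocol already ends treatment. No other wording in the table needs to change.

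The cost is a one-line amendment. No extra patients, visits or tests are needed, since hematology is already scheduled on Day 15 of Cycle 1 and Day 1 of Cycle 2 (Table 13). The downside is a slightly higher chance of stopping a level that would otherwise pass, and only because of a drug-related, life-threatening event.

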6.1.4 Dosing regimen

6.1.4.1 Ribociclib + Everolimus

The Barrow Neurological Institute / St. Joseph's Hospital and Medical Center will purchase commercially available supplies of ribociclib (Kisqali®) and everolimus (Afinitor®). Ribociclib+everolimus will be administered orally once daily on a 5-day dosing schedule during Phase 0 and a 28-day dosing schedule (3 weeks on, 1 week off) during Phase 2. The investigator must instruct the patient to take the treatment exactly as prescribed.

- Patients should take ribociclib+everolimus once daily at approximately the same time each day with a large glass of water (~ 250 ml) at the same time each day, in the morning, afternoon, or evening. The dose taken on the day of surgery will vary depending upon the planned time of the resection (see Section 4.1).
- Patients can take ribociclib+everolimus without regard to meals; however, dietary habits around the time of dosing should be as consistent as possible throughout the study.
- Patients should be instructed to swallow the ribociclib tablets whole and not to chew, crush or open them
- If vomiting occurs during the course of treatment, no re-dosing of the patient is allowed before the next scheduled dose.
- Any doses that are missed (not taken within 6 hours of the intended time) should be skipped and should not be replaced or made up on a subsequent day.
- Patients must avoid consumption of grapefruit, grapefruit hybrids, pomelos/pummelos, star-fruit, pomegranates or Seville oranges or products containing the juice of each during the entire study and preferably 7 days before the first dose of study medication, due to potential CYP3A4 interaction with the study medications. Orange juice is allowed.
- No herbal or dietary supplements known as strong inhibitors or inducers of CYP3A4 or those with a known risk of QT prolongation are permitted, due to potential interactions with ribociclib and everolimus; multivitamins are allowed.
- In Phase 2, Dose Levels 0-2, patients will take ribociclib+everolimus for 21 consecutive days followed by 1 rest week.
- In Phase 2, Dose Level 3, patients should take everolimus in two 5mg doses, approximately 12 hours apart (BID) for a total of 10mg. In Phase 0, the dose is 10mg given in one dose per day (qd).
- In Phase 2, Dose Level 4+, patients should take everolimus in one dose weekly. Ribociclib will be taken for 21 consecutive days followed by 1 rest week.

6.1.4.2 Additional Dosing Guidelines for Pharmacokinetic Sampling / ECG / Chemistry panel / Lipid Panel Collection

On days with PK, ECG sampling, chemistry panel and/or lipid panel sampling, the following additional guidelines should be followed:

- On a day when PK blood collection is scheduled at the clinic, patients must take study treatment in the clinic under the supervision of the Investigator or designee. On all other days, patients may take the study treatment at home.
- On a day of chemistry panel and/or lipid panel sampling, patients should be fasting from food and drink for at least 8 hours overnight; however, it will not be considered a deviation if the patient is not fasting. Water is allowed during all fasting periods; however, coffee, tea and juice are not permitted during the fasting period. Patients must also take study treatment in the clinic under the supervision of the Investigator or designee. On all other days, patients may take the study treatment at home.
- Pre-dose samples should be drawn prior to dosing. The sampling time of the PK samples and the dosing time must be precisely recorded in the CRF. Furthermore, the dosing date and time the study medication was taken on the day before the PK assessment must be precisely recorded in the CRF.
- Post-dose PK samples should be collected after dosing of the study treatment and precisely recorded in the CRF.
- If a pre-dose PK sample should be obtained, then the sample should be collected after the ECG and before dosing of the study treatment when possible; or allow approximately 30 minutes after the sample is drawn before obtaining the ECG.

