1.2.2.2 Clinical experience

1.2.2.2.1 Everolimus pharmacokinetics

Everolimus is rapidly absorbed with a median t_{max} of one to two hours. The steady-state $AUC_{0-\infty}$ is dose-proportional over the dose range between 5 to 70 mg when given weekly and 5 and 10 mg when given daily. Steady-state was achieved within two weeks with the daily dosing regimen.

C_{max} is dose-proportional between 5 and 10 mg for both the weekly and daily regimens. In healthy subjects, high fat meals reduced systemic exposure of a 10 mg dose of everolimus (as measured by AUC) by 22% and the peak plasma concentration C_{max} by 54%. Light fat meals reduced AUC by 32% and C_{max} by 42%. Food had no apparent effect on the post absorption phase concentration-time profile ([[Study RAD001C2120](#)]).

The blood-to-plasma ratio of everolimus, which is concentration-dependent over the range of 5 to 5,000 ng/mL, is 17% to 73%. The amount of everolimus confined to the plasma is approximately 20% at blood concentrations observed in cancer patients given everolimus 10 mg/day [DMPK R303044]. Plasma protein binding is similar in healthy patients and in subjects with moderate hepatic impairment (approximately 74%, [[Study RAD001A2303](#)]).

The major and nearly exclusive enzyme responsible for the metabolism of everolimus in man was CYP3A4 (DMPK(US)1998/005; DMPK(CH) R99-2448), ([Kuhn et al. 2001](#)). Other CYP isoenzymes either do not metabolize everolimus or do so at very low rates. Everolimus is a moderate inhibitor of P-glycoprotein-like mediated efflux systems, although the compound has a high intrinsic permeability when P-glycoprotein is inhibited ([Crowe 1998](#), [Laplante et al. 2002](#), [[DMPK\(CH\) 1997/417](#)]). Following oral administration, everolimus is the main circulating component in human blood and contributes the majority of the overall pharmacologic activity ([Study W107](#)). Everolimus was also shown to increase exposure of exemestane: In [[Study RAD001Y2301](#)], average exemestane C_{min} and C_{2h} were 45% and 71% higher, respectively, when co-administered with everolimus.

No specific excretion studies have been undertaken in cancer patients; however, data available from the transplantation setting found the drug to be mainly eliminated through the feces.

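### Meal state at the single Day 5 everolimus dose (Levels 4-6) is not controlled, which can add avoidable spread to the early Day 5 blood concentrations; a minor, optional refinement

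*Combined protocol and SAP*

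**What the plan says.** Section 1.2.2.2.1 gives the food data, which come from healthy volunteers: "high fat meals reduced systemic exposure of a 10 mg dose of everolimus (as measured by AUC) by 22% and the peak plasma concentration", the latter by 54%. For light-fat meals the reductions are 32% in AUC and 42% in Cmax. The same paragraph adds: "Food had no apparent effect on the post absorption phase concentration-time profile". Median tmax is one to two hours.

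The dosing rule in 6.1.4.1 is: "Patients can take ribociclib+everolimus without regard to meals; however, dietary habits around the time of dosing should be as consistent as possible". It also says: "The dose taken on the day of surgery will vary depending upon the planned time of the resection".

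Section 6.1.4.2 contains the only fast. On chemistry or lipid panel days, "patients should be fasting from food and drink for at least 8 hours overnight; however, it will not be considered a deviation" if they are not. Its PK-day guidance requires dosing and sampling times in the CRF but does not mention meals.

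Table 13 note 7 puts the pre-surgical panel on Day 4, with Day 5 allowed for Cohorts 1 and 2 and Day 6 for Cohort 3. At Levels 4-6, Table 7 note d gives everolimus once in Phase 0, on Day 5, and 4.1.1 moves serial blood PK to Day 5 (pre-dose, then 0.5 to 24 hours).

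**The concern.** The protocol documents a food effect on everolimus and then leaves food state open at the one Phase 0 everolimus dose that matters at Levels 4-6. When the dose and blood sampling moved to Day 5, the fast stayed with the chemistry panel, which by default is on Day 4, when these patients take no everolimus. For Cohort 3 neither permitted panel day is Day 5. Asking for consistent habits helps a patient who doses repeatedly; it cannot align a single dose across patients.

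What is at stake is precision in small groups. Levels may hold three patients, and 9.7 summarises concentrations by mean and 80% confidence interval. Section 2.3 says the 50-70 mg levels were added because of persistently negative everolimus PK, so exposure is the question they are meant to answer.

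**Working it through.** The plan has no figure of its own to reproduce here. The check has three steps.

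**1. Does the fast reach the dose?**

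| | Levels 0-3 | Levels 4-6 |
|---|---|---|
| Everolimus in Phase 0 | daily, Days 1-5 | once, Day 5 |
| Serial blood PK | Day 4 | Day 5 |
| Default panel day, hence requested fast | Day 4 | Day 4 |

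At Levels 0-3 the (unenforced) fast coincides with serial PK. At Levels 4-6 it does not, unless the panel is moved to Day 5, which is allowed for Cohorts 1 and 2 only.

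**2. How much spread could mixed meal state add?**

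Inputs from 1.2.2.2.1: fractional reduction f = 0.22 (AUC, high fat), 0.32 (AUC, light fat), 0.42 (Cmax, light fat), 0.54 (Cmax, high fat). Assumed, because the documents do not give it: p, the share of doses taken fed.

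Food-only CV = f·√(p(1−p)) / (1 − f·p). At p = 0.5 this is (f/2)/(1 − f/2):

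- AUC: 0.11/0.89 = 12.4%; 0.16/0.84 = 19.0%
- Cmax: 0.21/0.79 = 26.6%; 0.27/0.73 = 37.0%

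The maximum over all p is f/(2√(1−f)): for AUC at most 0.32/(2√0.68) = 19.4%; for Cmax at most 0.54/(2√0.46) = 39.8%. At p = 0 (everyone fasted) the added CV is zero.

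How much this matters depends on the background CV (CVb), also not given. Total CV = √((1+CVb²)(1+CVfood²) − 1), and at fixed n the interval half-width relative to the mean scales with it. At p = 0.5 the interval would widen by:

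| Assumed CVb | AUC | Cmax |
|---|---|---|
| 30% | 8.9-20.0% | 36-63% |
| 50% | 3.7-8.7% | 16-30% |
| 100% | 1.5-3.6% | 7-13% |

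These rows apply only if AUC and Cmax are derived and summarised; 9.7 names neither.

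**3. Does it reach tumour PK?**

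Positive PK (9.7.1) needs unbound drug in non-enhancing tumour above the in vitro IC50.

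- **Cohort 1** (1-3 hours after dosing) overlaps the 1-2 hour tmax. An effect is plausible, but at Levels 2+ this cohort opens only on expansion, with 4 patients.
- **Cohort 2** (7-9 hours) holds all escalation patients at Levels 2+. On the protocol's own statement about the post-absorption profile, the effect may be small or nil.
- **Cohort 3** (23-25 hours): the same reasoning applies, more strongly.

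If tissue did follow blood, a patient could turn negative when fed only if the fasted concentration lay between 1 and 1/(1−f) times IC50. That upper edge is 1.28 or 1.47 if tissue follows AUC, and 1.72 or 2.17 if it follows Cmax. The documents give neither IC50 nor tissue values, so the number of such patients cannot be computed.

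**The case against.** The strongest reply is that nothing the trial decides on is shown to be affected. Escalation follows DLT counts (Table 8). The optimal biological dose and Phase 2 entry use tumour PK and PD (6.1.2.1, 6.1.5), and escalation tissue at Levels 2+ is taken at 7-9 hours. Phase 2 blood sampling is trough only. Patients dosed on the day of surgery may be fasted anyway, which would put p near zero in Cohorts 1 and 2. Ribociclib's inhibition of everolimus metabolism (projected 3.5-fold AUC rise, 6.1.5) and the permitted phenytoin and carbamazepine (6.3.3.4) may matter more. Meals may be captured in the CRF, Dosing Diary or Laboratory Manual, which are not among the documents, and much of the dose rationale in 2.3 is redacted.

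Most of this stands, and it limits the weight of the point. It does not supply a food rule for the Day 5 dose. The pre-operative fasting argument is an assumption, since the documents state no such rule. If it holds, Cohort 3, dosed the day before surgery, could still differ in food state from the other two cohorts.

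A reader might also note that the AUC reductions of 22-32% exceed each step down the ladder (1 − 60/70 = 14.3%; 1 − 50/60 = 16.7%) and infer that food could blur or confound the dose levels. The documents do not support that. Nothing suggests that meal state differs by level. The food data are for 10 mg in healthy subjects. AUC "is dose-proportional over the dose range between 5 to 70 mg when given weekly", but this describes steady state, not a single dose, while Cmax "is dose-proportional between 5 and 10 mg for both the weekly and daily regimens" only.

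**Conclusion.** The gap is real but minor. At Levels 4-6, food state at the only Phase 0 everolimus dose is uncontrolled, and this can add between-patient variability to the early Day 5 blood concentrations, and to AUC and Cmax if derived.

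The size is uncertain. Food-only CV is about 12-19% for AUC and 27-37% for Cmax if half of doses are fed, at most 19.4% and 39.8% at any fed share, and near zero if patients are already fasted for surgery. These figures carry healthy-subject results at 10 mg over to ribociclib-treated patients at 50-70 mg, which is an assumption.

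It would be tempting to conclude that the primary tumour PK endpoint is compromised. The documents do not show this: an effect is plausible mainly in Cohort 1, and may be small or nil at 7-9 and 23-25 hours. The interval-widening figures should not be read as a forecast either, because both the fed share and the background CV behind them are assumed. This is an optional refinement, worth making because it is cheap.

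**What to change.** For patients still to be dosed at Levels 4-6:

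- Extend the 6.1.4.2 fast (at least 8 hours overnight, water allowed), or another single food condition compatible with pre-operative fasting, to the supervised Day 5 dose in all time cohorts, including Cohort 3.
- Exempt that dose from the 6.1.4.1 bullet that permits dosing irrespective of meals.
- Record the time and type of the last meal with the dosing time in the CRF, and list it with the PK results.

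Apply the same to the Day 4 and Day 5 doses at Levels 0-3 only if further patients are treated there.

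The cost is a sentence or two in 6.1.4 and one CRF field; Table 13 note 9 already has the Day 4 and Day 5 doses given in clinic. The downsides are one more instruction around surgery, and that patients already treated (2.3 implies the lower levels have been dosed) will not have followed it, so food state will not be uniform across the whole trial.
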